6.2. Primary and Supportive Estimands

There will be three estimands addressing different clinical questions of interest and intercurrent events for Induction Period. The estimands for Maintenance Period will be defined separately addressing different clinical questions of interest and intercurrent events for Maintenance Period.

6.2.1. Primary and Supportive Estimands for Induction Period

There will be three estimands of interest in analyzing primary and secondary endpoints for Induction Period. Two types of intercurrent events in terms of estimating the treatment effects for Induction Period will be considered, initiation of rescue medication as defined in Protocol Section 6.3 and permanent treatment discontinuation.

6.2.1.1. Primary Estimand (Hybrid)

The primary estimand is a hybrid estimand representing the primary clinical question of interest: what is the difference between treatment conditions, i.e., Lebrikizumab vs Placebo, in the target patient population, in successful responses or means after 16 weeks achieved without use of rescue medication and if all patients continued with treatment except those who discontinued due to lack of efficacy?

The primary estimand is described by the following attributes:

- A. Population: defined through appropriate I/E criteria to reflect the targeted patient population for approval
- B. Endpoint: apply to all primary and major secondary endpoints
- C. How to account for intercurrent events (ICEs)
 - a. Subjects who require any use of rescue medication or discontinue treatment due to lack of efficacy prior to week 16 will be considered as treatment failures, i.e., non-responder, after the ICEs. Therefore, composite strategy is used for these types of ICEs.
 - b. For subjects who discontinue treatment due to reasons other than lack of efficacy prior to week 16, a hypothetical strategy will be used to estimate what the treatment effect would have been if subjects continued with treatment. Therefore, hypothetical strategy is used for these types of ICEs.
- D. Population-level summary: difference in response proportions or means between treatment conditions

6.2.1.2. Supportive Estimand for Categorical Endpoints (Composite)

The supportive estimand for categorical endpoints is a composite estimand representing the supportive clinical question of interest: what is the difference between treatment conditions in

the target patient population, in successful responses after 16 weeks achieved without use of rescue medication or treatment discontinuation?

The supportive estimand is described by the following attributes:

- A. Population: defined through appropriate I/E criteria to reflect the targeted patient population for approval
- B. Endpoint: apply to categorical endpoints
- C. How to account for intercurrent events (ICEs)
 - a. Subjects who require any use of rescue medication or discontinue treatment prior to week 16 will be considered as treatment failures, i.e., non-responder, after the ICEs. Therefore, composite strategy is used for these types of ICEs.
- D. Population-level summary: difference in response proportions between treatment conditions

6.2.1.3. Supportive Estimand for Continuous Endpoints (Hypothetical)

The supportive estimand for continuous endpoints is a hypothetical estimand representing the supportive clinical question of interest: what is the difference between treatment conditions in the target patient population, in means after 16 weeks if rescue medication was not available and all patients adhered to the treatment?

The supportive estimand is described by the following attributes:

- A. Population: defined through appropriate I/E criteria to reflect the targeted patient population for approval
- B. Endpoint: apply to continuous endpoints
- C. How to account for intercurrent events (ICEs)
 - a. For subjects who require any use of rescue medication or discontinue treatment prior to week 16, a hypothetical strategy will be used to estimate what the treatment effect would have been if rescue medication was not available and all subjects adhered to the treatment. Therefore, hypothetical strategy is used for these types of ICEs.
- D. Population-level summary: difference in means between treatment conditions

Analytical details on how missing data including those as a result of intercurrent events will be handled for Induction Period can be found in Section 6.4.1. Detailed analyses relative to estimands including analysis type, method and imputation, population, time point, and treatment comparisons for efficacy/health outcomes analyses can be found in Section 6.11.

The following table (Table KGAB.6.3) summarizes the analytical strategies that will be conducted on the intercurrent events for the three estimands.

Table KGAB.6.3. Description of Primary and Supportive Estimands for Induction Period

Estimand	Analysis Strategy for Intercurrent Events			Missing Data Imputation Method
	Rescue Medication	Treatment Discontinuation		
		Due to lack of efficacy	Due to any other reasons	
Primary Estimand (Hybrid)	Composite: Set to baseline	Composite: Set to baseline	Hypothetical: Set to missing	Primary analysis: MCMC-MI Sensitivity analysis: tipping point analysis
Supportive Estimand for Categorical Endpoints (Composite)	Composite: Set to non-responder	Composite: Set to non-responder	Composite: Set to non-responder	NRI
Supportive Estimand for Continuous Endpoints (Hypothetical)	Hypothetical: Set to missing	Hypothetical: Set to missing	Hypothetical: Set to missing	MMRM, LOCF

Abbreviations: LOCF = last observation carried forward; MCMC-MI = Markov chain Monte Carlo multiple imputation; MMRM = mixed-model repeated measures; NRI = Nonresponder Imputation.

6.2.2. Primary and Supportive Estimands for Maintenance Period

There will be four estimands of interest in analyzing endpoints for Maintenance Period. Three types of intercurrent events in terms of estimating the treatment effects for Maintenance Period will be considered, initiation of rescue medication as defined in Protocol Section 6.3, permanent treatment discontinuation and transfer to escape arm.

6.2.2.1. Maintenance Primary Estimand (Hybrid)

The maintenance primary estimand is a hybrid estimand representing the clinical question of interest: what is the difference between treatment conditions, i.e., Lebrikizumab vs Placebo, in the target patient population, in successful responses or means after 52 weeks achieved without use of systemic rescue medication, without transferring to escape arm, if topical rescue medication were not available and if all patients continued with treatment except those who discontinued due to lack of efficacy?

The maintenance primary estimand is described by the following attributes:

- A. Population: Maintenance Primary Population as described in Section 6.1.1.
- B. Endpoint: apply to all major and other secondary endpoints for Maintenance Period
- C. How to account for intercurrent events (ICEs)
 - a. Subjects who require any use of systemic rescue medication, discontinue treatment due to lack of efficacy after week 16, or transfer to escape arm will be considered as treatment failures, i.e., non-responder, after the ICEs. Therefore, composite strategy is used for these types of ICEs.
 - b. For subjects who require any use of topical rescue medication, a hypothetical strategy will be used to estimate what the treatment effect would have been if

subjects continued with treatment. Therefore, hypothetical strategy is used for these types of ICEs.

- c. For subjects who discontinue treatment due to reasons other than lack of efficacy after week 16, a hypothetical strategy will be used to estimate what the treatment effect would have been if subjects continued with treatment. Therefore, hypothetical strategy is used for these types of ICEs.

D. Population-level summary: difference in response proportions or means between treatment conditions

6.2.2.2. Maintenance Supportive Estimand (Hybrid)

The maintenance supportive estimand for both continuous and categorical endpoints is a hybrid estimand representing the clinical question of interest: what is the difference between treatment conditions, i.e., Lebrikizumab vs Placebo, in the target patient population, in successful responses or means after 52 weeks achieved without use of systemic rescue medication, without transferring to escape arm, regardless of use of topical rescue medication and if all patients continued with treatment except those who discontinued due to lack of efficacy?

The maintenance primary estimand is described by the following attributes:

- A. Population: Maintenance Primary Population as described in Section 6.1.1.
- B. Endpoint: apply to all major and other secondary endpoints for Maintenance Period
- C. How to account for intercurrent events (ICEs)
 - a. Subjects who require any use of systemic rescue medication, discontinue treatment due to lack of efficacy after week 16, or transfer to escape arm will be considered as treatment failures, i.e., non-responder, after the ICEs. Therefore, composite strategy is used for these types of ICEs.
 - b. For subjects who require any use of topical rescue medication, observed data will be used. Therefore, treatment policy strategy is used for these types of ICEs.
 - c. For subjects who discontinue treatment due to reasons other than lack of efficacy after week 16, a hypothetical strategy will be used to estimate what the treatment effect would have been if subjects continued with treatment. Therefore, hypothetical strategy is used for these types of ICEs.
- D. Population-level summary: difference in response proportions or means between treatment conditions

6.2.2.3. Maintenance Supportive Estimand for Categorical Endpoints (Composite)

The maintenance supportive estimand for categorical endpoints only is a composite estimand representing the clinical question of interest: what is the difference between treatment conditions, i.e., Lebrikizumab vs Placebo, in the target patient population, in successful responses after 52

weeks achieved without use of topical or systemic rescue medication, treatment discontinuation or transferring to escape arm?

The maintenance supportive estimand for categorical endpoints is described by the following attributes:

- A. Population: Maintenance Primary Population as described in Section 6.1.1.
- B. Endpoint: apply to all major and other secondary categorical endpoints for Maintenance Period
- C. How to account for intercurrent events (ICEs)
 - a. Subjects who require any use of topical or systemic rescue medication, discontinue treatment after week 16, or transfer to escape arm will be considered as treatment failures, i.e., non-responder, after the ICEs. Therefore, composite strategy is used for these types of ICEs.
- D. Population-level summary: difference in response proportions between treatment conditions

6.2.2.4. Maintenance Supportive Estimand for Continuous Endpoints (Hypothetical)

The maintenance supportive estimand for continuous endpoints only is a hypothetical estimand representing the clinical question of interest: what is the difference between treatment conditions, i.e., Lebrikizumab vs Placebo, in the target patient population, in means after 52 weeks if rescue medication was not available and all patients adhered to the treatment and did not transfer to escape arm?

The maintenance supportive estimand for continuous endpoints is described by the following attributes:

- A. Population: Maintenance Primary Population as described in Section 6.1.1.
- B. Endpoint: apply to all major and other secondary continuous endpoints for Maintenance Period
- C. How to account for intercurrent events (ICEs)
 - a. For subjects who require any use of rescue medication, discontinue treatment after week 16, or transfer to escape arm, a hypothetical strategy will be used to estimate what the treatment effect would have been if rescue medication was not available and all subjects adhered to the treatment and did not transfer to escape arm. Therefore, hypothetical strategy is used for these types of ICEs.
- D. Population-level summary: difference in means between treatment conditions

Analytical details on how missing data including those as a result of intercurrent events will be handled for Maintenance Period can be found in Section 6.4.2. Detailed analyses relative to

estimands including analysis type, method and imputation, population, time point, and treatment comparisons for efficacy/health outcomes analyses can be found in Section 6.11.

The following table (Table KGAB.6.4) summarizes the analytical strategies that will be conducted on the intercurrent events for the four maintenance estimands.

Table KGAB.6.4. Analysis of Primary and Supportive Estimands for Maintenance Period

Maintenance Estimand	Analysis Strategy for Intercurrent Events				Transfer to escape arm	Missing Data Imputation Method
	Rescue Medication		Treatment Discontinuation			
	Topical rescue medication	Systemic rescue medication	Due to lack of efficacy	Due to any other reasons		
Maintenance Primary Estimand (Hybrid)	Hypothetical: Set to missing	Composite: Set to baseline	Composite: Set to baseline	Hypothetical: Set to missing	Composite: Set to baseline	MCMC-MI
Maintenance Supportive Estimand (Hybrid)	Treatment policy: as observed	Composite: Set to baseline	Composite: Set to baseline	Hypothetical: Set to missing	Composite: Set to baseline	MCMC-MI
Maintenance Supportive Estimand for Categorical Endpoints (Composite)	Composite: Set to nonresponder	Composite: Set to nonresponder	Composite: Set to nonresponder	Composite: Set to nonresponder	Composite: Set to nonresponder	NRI
Maintenance Supportive Estimand for Continuous Endpoints (Hypothetical)	Hypothetical: Set to missing	Hypothetical: Set to missing	Hypothetical: Set to missing	Hypothetical: Set to missing	Hypothetical: Set to missing	LOCF

6.3. Adjustments for Covariates

Unless otherwise specified, the statistical analysis models for the Induction Period efficacy and health outcome analysis will include the following stratification factors for Baseline randomization: geographic region (US versus EU versus rest of world), age (adolescent patients 12 to <18 versus adults ≥ 18 years) and baseline disease severity (IGA 3 versus 4).

The statistical analysis models for the Maintenance Primary Population (Maintenance Blinded Period) efficacy and health outcome analysis will include geographic region (US versus EU versus rest of world).

Below are the country allocations within each geographic region.

Table KGAB.6.5. Geographic Regions for Statistical Analysis

Geographic Region	Country or Countries
US	US
Europe	Estonia, France, Latvia, Lithuania, Poland, Spain
Rest of world	Canada, Australia, South Korea

In general, when an MMRM is to be used for analyses, baseline value and baseline-by-visit interactions will be included as covariates; when an ANCOVA is to be used for analyses, baseline value will be included as a covariate.

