**7.10. Week 16 ( $\pm$  3 Days) Transition to Maintenance Period**

- Administer the DLQI/CDLQI, and EQ-5D
- Administer the PROMIS measures
- Collect ACQ-5 for patients with comorbid asthma
- Complete the following assessments: IGA, BSA, EASI and SCORAD
- Perform a complete physical examination, including height and weight
- Review and record AEs and update concomitant medication and procedure/therapy information
- Review compliance report on the eDiary, confirm moisturizer use and remind patient to record the following: Pruritus and Sleep-Loss (daily), and POEM (weekly)
- Measure vital signs
- Draw pre-dose blood samples for laboratory tests, PK and ADA testing
- Collect a urine sample for urinalysis
- Conduct urine pregnancy test (WOCBP only)
- Re-randomize the patient to the Maintenance Period
- Train the patient to self-administer study drug
- Administer one injection and observe the patient self-injecting
- Dispense study drug for Week 18 injections

Sites collecting photos will also:

- Obtain a photograph of the target lesion

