## 9.3. Secondary Efficacy Analysis

For dichotomous secondary endpoints, the Cochran-Mantel-Haenszel analysis will be used.

For continuous secondary endpoints, an analysis of covariance (ANCOVA) will be used with factors of treatment and randomization strata (region, disease severity, age) and relevant baseline value.

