Statistical Analysis Plan (SAP) Version 4 was approved prior to Week 52 interim database lock and prior to the unblinding of the re-randomized maintenance treatment, but after the Lilly study team was unblinded to the induction treatment. This version of the SAP includes the following changes. Minor corrections/additions may not be included.

Revisions in SAP Version 4

Section	Description of Change	Rationale
Section 4, Section 6.11	
 Added “Time to loss of EASI-75 in the subset of patients who were re-randomized and achieved EASI-75 at Week 16 (EASI-75 calculated relative to baseline EASI score)” Updated “Time to loss of EASI-50 in the subset of patients who were re-randomized and achieved EASI-75 at Week 16 (EASI-50 and EASI-75 calculated relative to baseline EASI score)” to “Time to loss of EASI-50 in the subset of patients who were re-randomized at Week 16 (EASI-50 calculated relative to baseline EASI score)” Added “Percentage change in EASI score from Baseline at Week 52 in the 	
Added to allow analysis on time to loss of EASI-75
 
Modified to allow analysis on time to loss of EASI-50 on patients who were re-randomized at Week 16 as an overall evaluation of how soon those patients will move to escape arm
 
To reflect the change in the strategy of multiplicity control for EMA

	
subset of patients who were re-randomized at Week 16 ” as a major secondary endpoint for EMA
 
 Moved “Percentage change in SCORAD (having achieved EASI-75 at Week 16) from baseline at Week 52” from major secondary endpoints to other secondary endpoints 	
Section 6.3	
 Added specification of covariates to be adjusted for maintenance period analysis 	Clarification

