6.1.3. General Considerations for Analyses During Maintenance Period

Maintenance Period starts at the first injection of study treatment at Week 16 and ends on the date of Week 52 or the ETV (between Weeks 16 and 52) unless specified otherwise.

For the efficacy and health outcome analyses, baseline is defined as the last available value before the first injection in Induction Period and, in most cases, will be the value recorded at Baseline Visit (Day 1).

Unless otherwise specified, efficacy and health outcome scores at Week 16 prior to entering Maintenance Period will be presented for the visitwise reports for Maintenance Period.

Unless specified otherwise, for the safety analyses during Maintenance Period, baseline is defined as the last available value before first injection in Maintenance Period. In most cases, this will be the measure recorded at Week 16. For TEAEs, baseline is the events ongoing just prior to the first injection of the study drug injection at Week 16.

For patients in the Maintenance Primary and Secondary Population who met escape criteria (EASI-50 nonresponse) and escaped to lebrikizumab 250 mg Q2W at Weeks 24, 32, 40 and 48, only data in the Maintenance blinded period (up to the time of escape) will be included in both efficacy and safety analyses.

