6.1.3.1. Maintenance Primary Population

Unless otherwise specified, treatment comparisons of categorical efficacy and health outcomes variables will be analyzed using CMH test with treatment group and covariates as mentioned in Section 6.3 in the model. The CMH p-value will be reported, and the CMH adjusted odds ratio along with the 95% two-sided asymptotic (that is, not continuity corrected) CIs.

Each continuous efficacy and health outcomes measure score, change from baseline and percent improvement from baseline will be summarized by treatment group at all scheduled visits during Maintenance Period including Week 52, using descriptive statistics (n, mean, standard deviation (SD), median, minimum, and maximum).

Treatment comparisons for continuous efficacy and health outcome variables will be made using ANCOVA model as specified.

When the ANCOVA is used, the model will include treatment, baseline value and covariates as mentioned in Section 6.3. The ANCOVA analysis will be conducted as described in Section 6.1.2.

The KM product limit method will be used to estimate the survival for time to event analyses (e.g., time to loss of IGA response or time to loss of EASI-50 or time to loss of EASI-75). The stratified log-rank test will be performed with treatment group and covariates as mentioned in Section 6.3 in the model. A KM plot of the time to event by treatment group may be provided.

Unless specified otherwise, Fisher's exact test will be used for AEs and other categorical safety measures. Odds ratios will be created with lebrikizumab treatment as the numerator and placebo

as the denominator. Continuous vital sign and laboratory values will be analyzed by an ANCOVA model with treatment and baseline value as independent variables.

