A separate set of major secondary endpoints will be considered at Week 52 (End of Maintenance). These secondary endpoints across the 2 different regimens will be tested following the hierarchical testing procedure with a pre-specified order, that is, inferential conclusions about secondary endpoints require statistical significance at the 0.05 significance level.

The hierarchy for the major secondary endpoints at Week 52 is as follows

Q2W Maintenance therapy:

- Percentage of patients from those re-randomized to Q2W maintenance therapy having achieved EASI-75 at Week 16 who continue to exhibit EASI-75 at Week 52 (EASI-75 calculated relative to baseline EASI score).
- Percentage of patients from those re-randomized to Q2W maintenance therapy having achieved IGA 0 or 1 and a ≥ 2 -point improvement from Baseline at Week 16 who continue to exhibit an IGA 0 or 1 and a ≥ 2 -point improvement from Baseline at Week 52.

- Percentage of patients from those with a Pruritus NRS of ≥ 4 -points at baseline and re-randomized to Q2W maintenance therapy having achieved ≥ 4 -point reduction from baseline at Week 16 who continue to exhibit ≥ 4 -point reduction from baseline at Week 52.

Q4W Maintenance therapy:

- Percentage of patients from those re-randomized to Q4W maintenance therapy having achieved EASI-75 at Week 16 who continue to exhibit EASI-75 at Week 52 (EASI-75 calculated relative to baseline EASI score).
- Percentage of patients from those re-randomized to Q4W maintenance therapy having achieved IGA 0 or 1 and a ≥ 2 -point improvement from Baseline at Week 16 who continue to exhibit an IGA 0 or 1 and a ≥ 2 -point improvement from Baseline at Week 52.
- Percentage of patients from those with a Pruritus NRS of ≥ 4 -points at baseline and re-randomized to Q4W maintenance therapy having achieved ≥ 4 -point reduction from baseline at Week 16 who continue to exhibit ≥ 4 -point reduction from baseline at Week 52.

Q2W Maintenance therapy:

- Percentage change in EASI score from baseline at Week 52 for those patients re-randomized to Q2W maintenance therapy at Week 16.

Q4W Maintenance therapy:

- Percentage change in EASI score from baseline at Week 52 for those patients re-randomized to Q4W maintenance therapy at Week 16.

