	Proportion of patients maintaining IGA [0,1] with a ≥ 2 -point improvement from baseline among those re-randomized patients who achieved IGA [0,1] with a ≥ 2 -point improvement from Baseline at Week 16	Maintenance Supportive Estimand (Composite)	CMH analysis with NRI			Supplementary analysis
	Time to loss of IGA response	NA	KM method with log-rank test	Maintenance Primary Population who have achieved IGA [0,1] with a ≥ 2 -point improvement from Baseline at Week 16	Leb 250 mg Q2W vs PBO; Leb 250 mg Q4W vs PBO	Secondary analysis
	Proportion of patients with IGA [0,1] with a ≥ 2 -point improvement from baseline	NA	Descriptive statistics	Maintenance Secondary Population	No comparisons. all scheduled visits in Maintenance Period	Secondary analysis
	Proportion of patients with IGA [0,1] with a ≥ 2 -point improvement from baseline	NA	Descriptive statistics	Maintenance W16 Escape Population	No comparisons. all scheduled visits in Maintenance Period	Secondary analysis
	Proportion of patients with IGA[0,1] with a ≥ 2 -point improvement from baseline after lebrikizumab retreatment	NA	Descriptive statistics	Maintenance W24-48 Escape Population	No comparisons. Every 4 weeks after escape and re-treated by lebrikizumab 250mg Q2W	Secondary analysis

Measure	Variable	Estimand (Section 6.2)	Analysis Method (Section 6.1)	Population (Section 6.1.1)	Comparison/Time Point	Analysis Type
Eczema Area and Severity Index (EASI)	Change from baseline in EASI score Percent change from baseline in EASI score	Primary Estimand (Hybrid)	ANCOVA with MCMC-MI	ITT	Leb 250mg Q2W vs PBO; Week 16 and all scheduled visits in Induction Period	Key secondary analysis: percent change at Week 16; Secondary analysis: other timepoints
		Supportive Estimand (Hypothetical)	MMRM with observed data	ITT	Leb 250 mg Q2W vs PBO; Week 16 and all scheduled visits in Induction Period	Supplementary analysis
		Maintenance Primary Estimand (Hybrid)	ANCOVA with MCMC-MI	Maintenance Primary Population	Leb 250 mg Q2W vs PBO; Leb 250 mg Q4W vs PBO; all scheduled visits in Maintenance Period	Key secondary analysis: percent change at Week 52; Secondary analysis: other timepoints
		Maintenance Supportive Estimand (Hybrid)	ANCOVA with MCMC-MI			Supplementary analysis
		Maintenance Supportive Estimand (Hypothetical)	ANCOVA with LOCF			Supplementary analysis
		NA	Descriptive statistics	Maintenance W16 Escape Population	No comparisons. all scheduled visits in Maintenance Period	Secondary analysis

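### Free improvement (minor): the maintenance ANCOVA for Week 52 EASI percent change leaves out Week 16 EASI, which is measured before re-randomisation

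*SAP*

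**What the plan says.** **The model.** SAP 6.1.3.1: "When the ANCOVA is used, the model will include treatment, baseline value and covariates as mentioned in Section 6.3". For this period SAP 6.3 adds one covariate: "The statistical analysis models for the Maintenance Primary Population (Maintenance Blinded Period) efficacy and health outcome analysis will include geographic region". SAP 6.1.3 fixes the efficacy baseline: "baseline is defined as the last available value before the first injection in Induction Period", which is normally Day 1. The model is therefore treatment, Day 1 EASI and region.

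**Week 16 EASI.** Protocol 7.10 lists "Complete the following assessments: IGA, BSA, EASI and SCORAD" at the visit where the patient is re-randomised. Protocol 5.3 bases re-randomisation on the IGA or EASI score from that visit. Elsewhere the SAP presents Week 16 efficacy scores in visitwise reports, uses Week 16 as the usual maintenance baseline for safety (6.1.3), and lets post-baseline values into the imputation model (6.4.2.1). Nowhere does it put Week 16 EASI into the efficacy analysis model.

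**The endpoint.** SAP Table KGAB.6.12 classes it as "Key secondary analysis: percent change at Week 52", analysed by ANCOVA after multiple imputation. On testing, SAP 6.6.2 says: "These secondary endpoints across the 2 different regimens will be tested following the hierarchical testing procedure with a pre-specified order". Three Q2W responder tests come first, then three Q4W responder tests, then EASI percent change for Q2W and last for Q4W.

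**Background.** For continuous secondary endpoints, Protocol 9.3 says that "an analysis of covariance (ANCOVA) will be used with factors of treatment and randomization strata (region, disease severity, age) and relevant baseline value". The SAP revision history for Version 4 records "Added specification of covariates to be adjusted for maintenance period analysis". That version was approved before maintenance treatment was unblinded.

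**The concern.** Week 16 EASI is the most recent measure of disease before maintenance treatment is assigned, and it shows how deep each patient's response was. It plausibly predicts Week 52 EASI better than a Day 1 score taken before any treatment. The documents mention no stratification of the re-randomisation by Week 16 severity, and the placebo arm is the small one in a 2:2:1 split. Chance differences in Week 16 EASI between arms can therefore add noise that this covariate would partly remove. What is at stake is the width of the interval for Week 52 EASI percent change against placebo. It concerns the EMA maintenance family only, because FDA multiplicity control covers Induction Period endpoints (SAP section 4).

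**Working it through.** **1. The plan's own figures.** The plan gives no power or precision figure for the maintenance ANCOVA. Its only power statement (SAP 5.2: 96 versus 48 patients, more than 95%) reproduces with the continuity-corrected chi-square test: 95.1% for IGA 0/1 and 99.6% for EASI-75.

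**2. Arm sizes.** Lebrikizumab induction arm: 400 × 2/3 = 267. At the planning EASI-75 rate of 48.0%, 267 × 0.48 = 128 responders, split 2:2:1 into 51/51/26. At an assumed 60%, 160 responders split into 64/64/32. These are planning figures, not floors: the Maintenance Primary Population also requires a maintenance dose (Table KGAB.6.1), and patients missing Week 16 assessments because of COVID-19 may enter the escape arm (SAP 6.16.1).

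**3. Formula.** Let r be the partial correlation of Week 16 EASI with the outcome, given the existing covariates. The standard error is multiplied by about sqrt(1 − r²):
- r = 0.1: 0.5% reduction
- r = 0.2: 2.0%
- r = 0.3: 4.6%
- r = 0.4: 8.3%

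**4. What r might be.** The documents do not say, so every input here is assumed. All simulations admit responders only by percent EASI reduction, set failures to 0% change, fit one three-arm ANCOVA and omit multiple imputation.

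- *Grid of 54 scenarios:* two arm sizes; latent Week 16 to Week 52 correlation 0.3, 0.5 or 0.7; active/placebo failure 5/15%, 8/25% or 10/40%; logit slope of failure on Week 16 depth 0, 0.5 or 1.0 per SD. The model standard error ratio (with/without Week 16 EASI) for Q2W versus placebo was 0.930-0.999. By slope it was 0.975-0.999 at 0, 0.955-0.990 at 0.5 and 0.930-0.982 at 1.0. The empirical ratio was 0.915-1.005.
- *Second set:* arms 51/51/26; failure 5/20% or 10/35%. With latent correlation 0 to 0.5, the interval changed from 0.4% wider to about 8% narrower. At 0.7 it was about 1-11% narrower. With essentially no failures the change ran from 0.4% wider to 24% narrower.

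A working range is 0-8%, with values outside it possible in both directions.

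**5. Effect on the decision.** The test was gated on the two Week 52 EASI-75 comparisons, which are two of the six earlier tests. The chance of passing that gate and the Q2W percent-change test then moved by −0.6 to +0.6 percentage points (for example 36.7% to 37.1%, and 45.1% to 44.5%).

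**6. Is the standard error itself right?** SAP 6.2.2.1 and Table KGAB.6.4 set escape, systemic rescue and lack-of-efficacy discontinuation to baseline. If placebo fails more often, the smallest arm is also the most variable, and a pooled variance understates that. A simplified illustration counts only failure versus no failure, at the assumed 8% and 25%:
- variances: 0.08 × 0.92 = 0.0736 and 0.25 × 0.75 = 0.1875
- pooled: (102 × 0.0736 + 26 × 0.1875)/128 = 0.0967
- pooled squared SE: 0.0967 × (1/51 + 1/26) = 0.00562
- separate-variance squared SE: 0.0736/51 + 0.1875/26 = 0.00865
- ratio of SEs: sqrt(0.00562/0.00865) = 0.81

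In fuller simulations under the grid's failure assumptions, the model SE was about 9-18% below the empirical SE, with or without Week 16 EASI.

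**The case against.** The strongest case is that this is a preference. Protocol 9.3 asks for the relevant baseline value, SAP 6.1.3 defines it, and the endpoint is a change from that value. The tests come last of eight, the gated effect has mixed sign, and it models only two of the six gates. The size is assumed throughout. The simulated analysis is also not the planned one: multiple imputation is left out although data after topical rescue or other discontinuation are set to missing, and entry is by EASI-75 although IGA 0/1 also qualifies. Version 4 followed induction unblinding, so Week 16 EASI in the lebrikizumab arm could already be seen when covariates were chosen.

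Most of this stands as a limit on size and consequence. It does not remove the possible precision gain from a value already collected before assignment. Choosing the covariate with maintenance assignments still blinded would not be informed by the treatment comparison.

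Stronger readings are tempting and are not supported:
- **A conflict with the protocol, or a biased estimate.** The Day 1 value satisfies the wording of Protocol 9.3, and omitting a pre-randomisation covariate does not bias a randomised comparison. Protocol 9.3 also names disease severity and age, which the maintenance sentence in SAP 6.3 drops. That is a separate matter, and it does not make Week 16 EASI a required term.
- **A better chance of EMA success.** An ungated calculation gives −1.0 to +6.2 percentage points, but the test is never ungated.
- **Precision as the only issue with this ANCOVA.** Step 6 of the working shows why that cannot be asserted either.

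**Conclusion.** The point holds as a minor, optional improvement. The omission is plain from the SAP, and the covariate is legitimate because it precedes maintenance assignment. The likely benefit is a somewhat narrower interval: roughly 0-8% off the standard error under assumed correlations and failure patterns. It is near zero when failure does not depend on Week 16 EASI and larger when it does. An uninformative covariate would cost about 0.4% in interval width. No change in the confirmatory decision was demonstrated.

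If placebo failures set to baseline are more frequent, the pooled-variance standard error may be too small whichever covariates are used. The documents give no maintenance failure rates, so this is a possibility rather than a finding, and adding Week 16 EASI does not cure it.

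**What to change.** In SAP 6.1.3.1 and 6.3, add Week 16 EASI as a covariate alongside Day 1 EASI and region in the Maintenance Primary Population ANCOVA for Week 52 EASI percent change. State how a missing Week 16 EASI is handled for a patient re-randomised on IGA. The imputation model in SAP 6.4.2.1 already takes in post-baseline values, so naming Week 16 EASI there is only a clarification. If maintenance assignments are already unblinded, keep the planned model as primary and report the adjusted one as a labelled sensitivity analysis.

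The cost is one degree of freedom and a sentence in two sections. No new data are needed, and the difference-in-means summary in SAP 6.2.2.1 is unchanged. Version 4, which specified the maintenance covariates, was the natural place for it.
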